#### *Eligibility Phone Screening*

Trained study staff will review the eligibility criteria with potential participants. The potential participants' aMCI diagnosis will be verified by Epic chart review (if he/she is an MUSC patient) or by a formal request for medical records initiated by the patient and provided to study staff. PI and neuropsychologist [name] will personally review all potential participants' medical records to ensure that each MCI patient will meet the detailed inclusion/exclusion criteria, which necessitates that the patient has a comprehensive clinical history and neuropsychological test results on file. Should a potential participant not have an established MCI diagnosis, or have incomplete data in support of this diagnosis to the extent that his/her eligibility cannot be readily ascertained, study staff will recommend that he/she complete a clinical evaluation with a clinical neuropsychologist at MUSC or elsewhere, as convenient to him/her.

## **9.0 CONSENT PROCESS**

Following recruitment and screening, the potential participant will be given a copy of the informed consent form (ICF) in-person, via postal mail, or e-mail for review. There is no required timeline between their receipt of the ICF and deciding whether or not to participate. Participants will be encouraged to take their time to decide.

Informed consent will take place on the MUSC campus or through telehealth by trained research staff (eConsent). If consenting through telehealth using an IRB-approved electronic/online platform (i.e. REDCap or [musc.doxy.me](http://musc.doxy.me); all future references to an "electronic/ online platform" hereafter refer to these), the study staff will first confirm that participants have the appropriate technology to complete the electronic consent process. In the case of eConsent, the participant will be asked to locate a private and interruption-free environment in order to complete the appointment. The participant will receive a copy of the signed e-consent by email from the research personnel. If consenting in-person, the visit will take place in laboratory or Center for Biomedical Imaging space at [name].

To ensure ongoing consent, participants will be queried at the start of any procedure about their comfort and willingness to continue.

## 10.0 STUDY DESIGN AND METHODS

A summary and timeline of all procedures are outlined and described below.

Session Number	Task Description	Location	Approximate Time Commitment
0	Screening Epic and/or medical record review Keel TMS Safety Screen	Telephone	30 minutes
1	Pre-treatment Neurocognitive/Neuropsychiatric Assessment 
Consent/Safety Consent* Keel TMS Safety Screen* TMS Motor Threshold Test Credibility/Expectancy Questionnaire (Pre-treatment)
 
Cognition Montreal Cognitive Assessment (MoCA) NIH Cognition Toolbox NINDS-CSN 30-Minute Neuropsychological Protocol (Hachinski et al., 2006, which includes Semantic and phonemic fluency, Digit Symbol-Coding, Digit Span, Hopkins Verbal Learning Test-Revised, Trail Making Test) WASI-II (Vocabulary, Matrix Reasoning)*
 
Affective Function/Quality of Life Lawton Instrumental Activities of Daily Living Scale (IADL)* Mini-International Neuropsychiatric Interview (M.I.N.I.)* Columbia Suicide Severity Rating Scale (CSSRS) Geriatric Depression Scale (GDS)* Hamilton Depression Rating Scale (HAM-D)* Young Mania Rating Scale (YMRS)* PROMIS Measures: Anxiety, Depression, Applied Cognitive Abilities, Social Participation, General Life Satisfaction, and Fatigue*
	Center for Biomedical Imaging	3 – 3.5 hours
2	Pre-treatment MRI Scans FLAIR, diffusion, T2*/gradient, volumetric scans, resting-state fMRI	Center for Biomedical Imaging	1 – 2 hours
3-5	rTMS Treatment Sessions Review of systems adverse events questionnaire (Yaejee et al., 2015) Momentary Assessment of TMS 8, 3 min sessions rTMS, interspersed with BrainHQ exercises	Center for Biomedical Imaging	2 – 3 hours per day, for 3 days within a 8-day span
6	Post-treatment Neurocognitive/Neuropsychiatric Assessment 
Cognition NIH Cognition Toolbox Montreal Cognitive Assessment (MoCA) NINDS-CSN 30-Minute Neuropsychological Protocol (Hachinski et al., 2006)
 
Affective Function/Quality of Life Lawton Instrumental Activities of Daily Living Scale (IADL)* Mini-International Neuropsychiatric Interview (M.I.N.I.)* Columbia Suicide Severity Rating Scale (CSSRS) Geriatric Depression Scale (GDS)* Hamilton Depression Rating Scale (HAM-D)* Young Mania Rating Scale (YMRS)* PROMIS Measures: Anxiety, Depression, Applied Cognitive Abilities, Social Participation, General Life Satisfaction, and Fatigue*
	Center for Biomedical Imaging	2 - 3 hours

	Credibility/Expectancy Questionnaire (Post-treatment)* TMS Experience Questionnaire* BrainHQ Experience Questionnaire* Review of systems adverse events questionnaire (Yaejee et al., 2015)		
7	Post-treatment MRI Scans FLAIR, diffusion, T2*/gradient, volumetric scans, resting-state fMRI	Center for Biomedical Imaging	1 - 2 hours
8	1 – 3 weeks post-treatment completion Review of systems adverse events questionnaire (Yaejee et al., 2015) PROMIS Measures: Anxiety, Depression, Applied Cognitive Abilities, Social Participation, General Life Satisfaction, and Fatigue*  BrainHQ exercises	REDCap  Online	10 – 20 minutes  >20 minutes per day
9	4 weeks post-treatment completion PROMIS Measures: Anxiety, Depression, Applied Cognitive Abilities, Social Participation, General Life Satisfaction, and Fatigue* Montreal Cognitive Assessment (MoCA)* TMS Experience Questionnaire* BrainHQ Experience Questionnaire*	REDCap  Video Conference	30 min – 1 hour

\*Option to complete remotely, such as due to COVID-19 precautions. Components of sessions 1&2 and 6&7 may be combined..

**Session 1: In-person Pre-treatment Neurocognitive/Neuropsychiatric Assessment (2 - 3 hours).** Participants will complete computerized cognitive tests from the NIH Toolbox (30-40 minutes). Each of these tests has been extensively normed, compared to traditional neuropsychological measures. Tests from different batteries will be utilized in this study for optimizing a comprehensive but efficient, reliable, and minimally burdensome subset of tests for MCI patients.

For further sample characterization with more traditional and more extensively normed neuropsychological measures, participants will complete the Montreal Cognitive Assessment (MoCA) and the 30-minute battery recommended by the National Institute of Neurological Disorders and Stroke-Canadian Stroke Network (NINDS-CSN) Vascular Cognitive Impairment Harmonization Standards: Semantic and phonemic fluency, Digit Symbol-Coding, Digit Span, Trail Making Test A & B, and Hopkins Verbal Learning Test-Revised. Full scale IQ will be assessed with the Vocabulary and Matrix Reasoning subtests of the WASI-II.

During this session, the Lawton Instrumental Activities of Daily Living Scale (IADL) will be administered in order to verify the participants' functional independence per MCI criteria.

To assess neuropsychiatric symptoms and conditions often concomitant with aMCI, participants will then complete the Mini-International Neuropsychiatric Interview (M.I.N.I). The Columbia Suicide Severity Rating Scale (CSSRS) will be administered in order to assess suicide risk. The Geriatric Depression Scale (GDS) Hamilton Depression Rating Scale (HAM-D), and Young Mania Rating Scale (YMRS) will be administered. The computer adaptive test versions of the Anxiety, Depression, Applied Cognitive Abilities, Social Participation and Fatigue PROMIS Measures will also be administered. The PROMIS measures have been selected, specifically for the low-burden nature of the computerized adaptive form and the extensive normative data. Neuropsychiatric conditions other than psychotic disorders and substance use disorders will not

result in exclusion. The Edinburgh Handedness Inventory will be administered to assess hand preference on several forms of manual activity.

The option to remotely complete the M.I.N.I, MoCA, WASI-II, Demographics, Keel TMS Safety Screen, IADL questionnaire, GDS, HAM-D, YMRS, and the PROMIS measures will be given to participants if they are unable to physically come to the Center for Biomedical Imaging for the time being, such as due to COVID19 precautions. Phone calls or video conferencing through musc.doxy.me will be utilized in order to administer and oversee the completion of these assessments.

Comfort and reliability considerations: During the administration of some of the neuropsychological assessments, the participants' verbal responses will be audio recorded for quality control purposes. During all in-person sessions, snacks and water will be offered between testing administrations in order to improve energy, limit fatigue, and promote comfort. Furthermore, multiple breaks will be offered. Finally, participants will be given the option to schedule sessions on the same day, with a break, if additional visits/travel would be burdensome.

**Session 2: MRI Scanning (1 - 2 hours).** At pre- and post-treatment participants will complete FLAIR, diffusion, T2\*/gradient, perfusion and volumetric scans for assessment of structural changes. Participants will also complete a resting-state fMRI scan.

**Sessions 3-5: rTMS (2 – 3 hours).** A MagVenture MagPro TMS System will be utilized. All participants will receive open-label treatment for approximately eight, 3-minute sessions of intermittent theta burst rTMS on each of three days within an eight-day span. A single session=600 pulses at 120% rMT, iTBS triplets at 50 Hz for 2 s and repeated every 10 s for a total of 190 s to left dlPFC. Total pulses=14,400. To enable adherence and retention, the days do not need to be contiguous. Same day sessions will be separated by 10-15 minutes, but more accounting for participant comfort. After each day of treatment, participants will be asked to complete an rTMS acceptability questionnaire. During treatment breaks participants will complete Momentary Assessment of TMS and 10-15 minutes of Brain HQ exercises between each session and will also have the option of completing tasks at home on intervening days during the treatment schedule. At the end of the final treatment session, participants will be asked to rate the exercises based on difficulty and enjoyment.

**Session 6: In-person Post-treatment Neurocognitive/Neuropsychiatric Assessment (2 - 3 hours).** Within one week following treatment, participants will repeat the pre-treatment neuropsychiatric and neurocognitive assessment for assessment of pre/post treatment changes.

**Session 7: Post-treatment MRI Scans (1 - 2 hours).** Within one week following treatment, participants will repeat the pre-treatment MRI scans for assessment of pre/post treatment changes.

**Session 8: 1 – 3 weeks post-treatment completion.** During the intervening weeks after Sessions 6/7 and before Session 9, the participants will be asked to remotely complete surveys using REDCap. Participants will also be provided with a research account for BrainHQ and asked to engage in at least 20 minutes of brain exercises daily until Session 9.

**Session 9: 4 weeks post-treatment completion.** Participants will again be asked to complete surveys using REDCap. Participants will also be asked to complete the MoCA remotely, as well as acceptability/satisfaction questionnaires regarding the rTMS and BrainHQ interventions.

**Participant Compensation.** Participants will be compensated as follows:

Consent & Session 1:	\$40 for screening and pre-treatment assessments
Session 2:	\$50 for the pre-treatment MRI
Sessions 3 to 5:	\$120 for rTMS treatment (i.e. \$40/day)
Sessions 6 and 7:	\$100 for post-treatment assessments and MRI
Session 8:	\$42 for post-treatment questionnaires (i.e. \$14/wk over 3 weeks)
Computerized Exercises:	\$4.5/completed 20-minute session (up to \$126)
Session 9:	\$22 for post-treatment questionnaires at 4 weeks follow-up
Total:	\$500 per participant upon the completion of all procedures.

You will receive payments after completion of each Session and after 3 days of TMS. Payment for study visits will be made using a pre-paid debit card, called a ClinCard. It works like a bank debit card and participants may use the card to purchase goods or services everywhere Debit MasterCard is accepted. Participants will be given a ClinCard at the beginning of the study. Each time they receive payment for participation in this study, the money will be added to the card, as outlined in the payment schedule above. In the event that any portion of the study is completed remotely, the ClinCard will be mailed to the participant.

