## **4.0 STUDY ENDPOINTS**

### **AIM 1: Establish the safety of an accelerated rTMS protocol for neurocognitive rehabilitation in aMCI.**

Primary Outcomes: Clinically significant structural brain changes; Neurocognitive performance changes; Adverse events

Secondary Outcomes: Psychopathology symptom changes

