## 11.0 SPECIMEN COLLECTION AND BANKING (Not Applicable)

## 12.0 DATA MANAGEMENT

### *Analysis*

Aim 1. FLAIR, diffusion, T2\*/gradient, perfusion and volumetric scans will be reviewed by [name] for any new signal abnormality. Adverse events will be surveyed and summarized.

Aim 2. Retention (i.e., defined as completion of all study sessions) will be determined. Participants will also complete a survey regarding acceptability, including qualitative responses for treatment modification.

Exploratory Aim 3. Neurocognitive performance and affective symptoms/quality of life will be analyzed with repeated-measures mixed models.

Exploratory Aim 4. BrainHQ usage/retention, performance, and acceptability will be analyzed with repeated-measures mixed models.

**Power Considerations.** The aims of this study are to determine safety and feasibility. The retention rate of 80% was determined to ensure that recruitment in the planned follow-up studies would be feasible in the longer time span allowed by future grants. Although these results will not be as compelling in the absence of a sham control, these data will give us an estimate of the

potential effect sizes and response variability that we can anticipate in future randomized controlled trials.

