Consent and HIPAA forms will be kept on file for 6 years. Contact information is kept on file for 6 years if the participant consents to allowing their information to remain active in our files, or the contact information is destroyed immediately after the study is completed if participants chose that option on the consent form. Although individual-subject analyses may be written up in publications, the individual subjects producing that data will never be identified by name or initials, or any other identifying information.

*Other protections against risk.* In designing this trial, the research team sought to maximize data collection within the overall priority of maintaining participant comfort and safety. As was discovered in the pilot study by George and colleagues, the proposed design is feasible, does not impose unreasonable expectations of time or effort, or expose patients to risks or limit them from the best available care. In the very unlikely event that a subject endorses transient alcohol or substance abuse during the course of this study, the coordinator will confer with a physician co-investigator prior to proceeding with any treatment.

*Adverse Events & Trial Safety.* Potential conflicts of interest will be reported using the NIH rules for disclosure. Adverse Events (AEs)/Serious Adverse Events (SAEs) occurring during the course of the project will be collected, documented, and reported in accordance with protocol and IRB reporting requirements. All research staff involved with adverse event reporting will receive general and protocol specific AE/SAE training including identification, assessment and evaluation, and documentation and reporting. Any potential adverse events will be identified during the course of the study from participant self-report and administration of the visit assessments and procedures. Research staff will identify adverse events and obtain all available information to assess severity, seriousness, study relatedness, expectedness, outcome and the need for change or discontinuation in the study intervention.

An Adverse Event (AE) is defined as any unwanted change, physically, psychologically or behaviorally, that occurs in a study participant during the course of the trial is an adverse event. A Serious Adverse Event (SAE) is defined as an adverse event that has one of the following outcomes:

- Results in death,
- Is life-threatening,

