Potential worsening of neuropsychiatric symptoms with TMS. Several studies have thus far demonstrated the feasibility of using rTMS in depression without any alarming indicators of exacerbation of symptoms. The research team will work closely with patients to familiarize them with the nature of this experimental setup. All staff will also be trained to be alert to any worsening of neuropsychiatric symptoms and/or psychosocial impairment. Bipolar patients have at times shown hypomanic or manic switches in the course of once-daily rTMS, as such patients with bipolar type I will be excluded. Additionally, all patients will be assessed throughout each day for worsening symptoms. Participants will similarly be queried for worsening suicidal ideation/intent. Drs. [name] or [name] will additionally assess each patient once per week in-person or via telephone during rTMS treatment and the one month study involvement to assess mood, functioning, and safety.

Potential risk of a seizure with TMS. There is a risk that TMS can cause a seizure; but it is rare. The risk of seizure induction is related to the intensity, duration, frequency and rest interval of stimulation. Following the adoption and widespread use of the safety guidelines from a National Institute of Neurological Disorders and Stroke (NINDS) workshop on TMS, only 20 seizures have been reported since 1997, and they usually involved parameters of "higher settings" than the "safe range". To our knowledge, stimulation with the parameters and settings proposed in this study should not cause seizures. Each subject's stimulus intensity is determined by his or her motor threshold and will be carefully calculated before beginning treatment. In this study participants will receive rTMS to the prefrontal cortex, a region far less prone to seizure. Nonetheless, we will watch participants closely for any signs of seizure throughout all procedures. Additionally, our study patients will be free from using known stimulants and medications that are known to increase the risk of seizure (e.g., theophylline).

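### The structured adverse-event questionnaire has no specified reading before the first stimulation and is not repeated at Session 9, so physical symptoms lack a scheduled within-person baseline

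*Combined protocol and SAP*

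**What the plan says.** Section 4.0 names three primary outcomes for Aim 1: "Clinically significant structural brain changes; Neurocognitive performance changes; Adverse events". For the third, the schedule table in Section 10.0 provides one structured instrument, the "Review of systems adverse events questionnaire". It is listed for the three treatment days, the post-treatment assessment and the weeks 1-3 follow-up. It is not listed at telephone screening, at the pre-treatment assessment or at the pre-treatment MRI visit. It is also not listed at Session 9, headed "4 weeks post-treatment completion".

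Section 13.0 gives the definition: "An Adverse Event (AE) is defined as any unwanted change, physically, psychologically or behaviorally", arising during the trial. The same section says that events are picked up from what participants report and from the visit assessments. Section 15.0 adds checks for worsening symptoms through each treatment day, and says that a study doctor will "assess each patient once per week in-person or via telephone during rTMS treatment and the one month study involvement".

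The analysis in Section 12.0 is one sentence: "Adverse events will be surveyed and summarized".

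**The concern.** An event defined as a change needs a state to change from. There is no sham group, so each participant's own earlier reading is the only structured reference available. If the first form is completed after stimulation has begun, a long-standing headache and one that began with treatment look the same on it. Sorting them then depends on recall and staff judgement. Recall is a weak basis here: participants are aged 60-85, and inclusion criterion iv requires impairment in the memory domain.

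The error could go either way: existing complaints could be counted as events, or real events could be put down to history. At stake are the Aim 1 hypothesis of no significant adverse events and the descriptive event table that later trials would build on. At the other end of follow-up, participants are asked to do daily home exercises until Session 9, but the questionnaire series stops a week earlier.

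**Working it through.** The plan states no rate, power or sample-size figure for this point, so there is nothing to reproduce. The check is a reading of the schedule, followed by an illustration.

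**1. Where the questionnaire appears (Section 10.0 table).**

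| Session | Content | Questionnaire listed |
|---|---|---|
| 0 | Screening | No |
| 1 | Pre-treatment assessment | No |
| 2 | Pre-treatment MRI | No |
| 3-5 | Treatment days | Yes, timing not stated |
| 6 | Post-treatment assessment | Yes |
| 7 | Post-treatment MRI | No (Session 6 covers this period) |
| 8 | Weeks 1-3 | Yes |
| 9 | Week 4 | No |

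**2. Comparison with the other instruments.** The cognitive tests (MoCA, NIH Toolbox, NINDS-CSN battery), IADL, M.I.N.I., CSSRS, GDS, HAM-D, YMRS and PROMIS, including Fatigue, are all listed at both Session 1 and Session 6. The expectancy form has a pre-treatment and a post-treatment version. The MRI sequences in the table are the same at Sessions 2 and 7. Leaving aside the experience questionnaires, which can only follow treatment, the adverse-event form is the one Session 6 measure with no pre-treatment counterpart.

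**3. Timing at Session 3.** In the Sessions 3-5 row the form is the first item, ahead of the stimulation item. The Sessions 3-5 narrative does not mention it. A reading before the first rTMS session is therefore neither specified nor ruled out. Session 1 also includes a TMS motor threshold test, so a baseline free of any TMS would have to precede that.

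**4. Week 4.** The week without the form is 7 of 28 follow-up days, or 25%. The weekly doctor contact and self-report run through that week. PROMIS and the MoCA are collected at Session 9.

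**5. Illustration.** Assume that a proportion p of participants has a given symptom before treatment. The documents give no such prevalence. The expected number with it is n × p, and the chance that at least one has it is 1 − (1 − p)^n. Section 6.0 gives n = 30 completers and 40 enrolled.

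| p (assumed) | Expected, n = 30 | P(at least one), n = 30 | Expected, n = 40 | P(at least one), n = 40 |
|---|---|---|---|---|
| 0.05 | 1.5 | 0.785 | 2 | 0.872 |
| 0.10 | 3 | 0.958 | 4 | 0.985 |
| 0.20 | 6 | 0.999 | 8 | >0.999 |
| 0.30 | 9 | >0.999 | 12 | >0.999 |

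These are participants who could endorse the symptom on a treatment-day form with no treatment effect. They are not a count of misclassified events.

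**The case against.** The case against has real force on four points.

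- **Separation of new from existing symptoms.** A reader might infer that the study cannot tell them apart. The documents do not support that. The Session 3 form may come before stimulation, a stable existing complaint does not meet the Section 13.0 definition, and staff must assess each event's relatedness and expectedness. A ticked item on a checklist is not automatically an adverse event.
- **The last week.** A reader might infer that week 4 has no safety coverage. It has the weekly doctor contact, self-report and a video contact at Session 9. Only the structured form is missing.
- **Scope.** Adverse events are one of three Aim 1 primary outcomes, and the other two have pre-treatment readings. Fatigue, affective symptoms, suicidality, mania and cognition also have Session 1 readings. The gap is mainly in physical symptoms.
- **Size.** The prevalences are assumed. The form is not reproduced in the documents, so its recall period and any attribution items are unknown. If it asks only about new symptoms, the illustrative counts would overstate the problem.

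What the objection does not remove is that no baseline reading is specified and no summary rule refers to one. The weekly contact covers mood, functioning and safety in general terms and is not tied to this checklist, so the documents give no basis for treating it as a continuation of the questionnaire series. It is also absent from the schedule table.

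**Conclusion.** The point holds in limited form. The structured form has no specified administration before stimulation, is not repeated at Session 9, and feeds an analysis with no rule for new or worsened symptoms. The adverse-event component of Aim 1 therefore lacks a scheduled within-person reference for physical symptoms such as headache. This does not invalidate the safety assessment, which has several other channels. It weakens one of them where a remedy is cheap.

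The size cannot be established from the documents. The 3-9 of 30 completers at 10-30% prevalence is illustrative only. The conclusion rests on the schedule table being the full list of administrations. If the Session 3 form was always meant as the baseline, the remaining defect is that the protocol does not say so or use it that way. A baseline would separate existing from new symptoms. It would not show that new ones were caused by treatment, which a single-arm study cannot settle.

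**What to change.** 1. List the same questionnaire at Session 1, ideally before the motor threshold test. Alternatively, specify that the Session 3 form is completed before the first stimulation. Designate that reading as baseline.
2. Add one sentence to the Aim 1 analysis in Section 12.0: questionnaire symptoms are summarised as new or worse than the baseline reading, with the number of participants who have a baseline form as the denominator.
3. Add the form to the Session 9 REDCap set.
4. Enter the weekly doctor contact described in Section 15.0 in the schedule table, so that the two sections agree.

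The cost is a few more minutes of participant time at existing contacts, an edit to the schedule table and one analysis sentence. A baseline cannot be recovered for anyone already treated without one; those participants should be reported separately.

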## 5.0 INCLUSION AND EXCLUSION CRITERIA/STUDY POPULATION

Participants will be recruited through outpatient memory disorders and neuropsychology clinics staffed by neurologists and neuropsychologists at MUSC/DVA. (No procedures will be performed at the DVA; only recruitment materials will be provided.) Clinic providers will be trained on study criteria and procedures and will be provided with recruitment materials. [name] will oversee recruitment and will ensure that participants meet the following eligibility criteria:

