### Exclusion Criteria:

- i. Dementia diagnosis per DSM-5 or NIA-AA criteria.
- ii. Daily/weekly use of anticholinergics, neuroleptics, sedatives, or bupropion. Stimulant use may be allowed pending investigator review. Cholinesterase inhibitors, NMDA receptor

antagonists, and antidepressants are allowed if on a stable regimen of four weeks prior to enrollment.

- iii. History of significant or unstable condition/s that may impact cognition such as significant cardiac, cerebrovascular, or metabolic disease, severe mental illness (e.g. bipolar disorder, psychoses), alcohol or substance use disorder, developmental disorder, or other neurologic disease (e.g. severe brain injury, seizures).
- iv. MRI and TMS contraindications (e.g., implants, claustrophobia, conditions/treatments that lower seizure threshold, taking medications that have short half-lives, no quantifiable motor threshold, active substance use disorder, bipolar disorder).
- v. Is enrolled in a clinical trial and/or has received an investigational medication within the last 30 days.

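### Bipolar disorder is a listed TMS contraindication in Section 5.0, but the Session 1 rule in Section 10.0, read literally, keeps a participant in whom it is first detected there, and Section 15.0 names only type I

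*Combined protocol and SAP*

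**What the plan says.** Section 5.0, Exclusion Criteria, mentions bipolar disorder twice. Criterion iii covers a history of significant or unstable conditions that could affect cognition, and includes "severe mental illness (e.g. bipolar disorder, psychoses" among its examples. Criterion iv lists MRI and TMS contraindications, among them "no quantifiable motor threshold, active substance use disorder, bipolar disorder". Neither entry is limited to a type of bipolar disorder.

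Section 5.0 also says that a named overseer "will oversee recruitment and will ensure that participants meet the following eligibility criteria". Under Eligibility Phone Screening in Section 8.0, the PI "will personally review all potential participants' medical records to ensure that each MCI patient will meet the detailed inclusion/exclusion criteria".

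In the Section 10.0 schedule, Session 0 is a telephone step consisting of "Epic and/or medical record review Keel TMS Safety Screen". The M.I.N.I. and the mania scale first appear at Session 1. The Session 1 text describes the M.I.N.I., says that the "Young Mania Rating Scale (YMRS) will be administered", and shortly afterwards states: "Neuropsychiatric conditions other than psychotic disorders and substance use disorders will not" lead to exclusion (the sentence finishes after a page break).

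Section 15.0, on possible worsening of neuropsychiatric symptoms, reports that bipolar patients have sometimes switched to hypomania or mania during once-daily rTMS. It gives this as the reason for excluding patients with bipolar type I.

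Section 14.0 allows, but does not oblige, the PI to discontinue a subject who entered in violation of the protocol, whose best interest is not served by continuing, or who develops mania or hypomania.

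**The concern.** Session 1 is the first scheduled structured psychiatric interview, and it comes before any stimulation. It is where bipolar disorder missing from the medical record would be most likely to come to light while exposure can still be avoided. The one sentence in Section 10.0 that says how to handle neuropsychiatric findings at that visit points the opposite way from criterion iv.

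Aim 1 is safety, and the protocol itself links bipolar disorder to mood switching under rTMS. Staff who followed the Session 1 sentence as written would treat someone whom the eligibility list calls contraindicated.

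**Working it through.** The plan gives no figure to reproduce here. The check is a side-by-side reading of the statements, applied to one case: bipolar disorder first identified at Session 1.

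| Place | Rule as written | Type I | Type II or other |
|---|---|---|---|
| Section 5.0, criterion iv | Bipolar disorder is a listed contraindication, no type given | Excluded | Excluded |
| Section 5.0, criterion iii | Example of severe mental illness, within significant or unstable conditions that may affect cognition | Excluded if that qualifier is met | Excluded if that qualifier is met |
| Section 10.0, Session 1 | Only psychotic and substance use disorders exclude | Not excluded | Not excluded |
| Section 15.0 | Type I excluded | Excluded | Not named |

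1. Criterion iv is the unqualified statement. Criterion iii supports it but carries its own qualifier, so the conflict rests mainly on iv.
2. The exception in Section 10.0 has two members, psychotic disorders and substance use disorders. Bipolar disorder is not one of them. Criterion iii lists bipolar disorder and psychoses as separate items, so the protocol's own usage does not fold one into the other. At most, bipolar disorder with psychotic features might be read as covered.
3. Section 15.0 is narrower than criterion iv. It is silent on type II and does not permit it.
4. Timing: Session 1 is assessment, Session 2 is MRI, and Sessions 3 to 5 are rTMS. Removal under Section 14.0 is therefore possible before exposure, but it is worded as something the PI may do.
5. Exposure if the participant is kept: 3 days × 8 sessions = 24 sessions, and 24 × 600 pulses = 14,400 pulses. This matches the Section 10.0 statement "Total pulses=14,400".
6. Monitoring after that point: Section 15.0 provides symptom checks through each treatment day and a weekly assessment that covers mood. Both act once stimulation has begun. The mania scale is scheduled at Sessions 1 and 6, and at none of the three treatment days.

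The documents do not say how often undocumented bipolar disorder would be found in this population, so no expected count is given.

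**The case against.** The strongest reply is that the Session 1 sentence was never meant to override Section 5.0. It does not mention bipolar disorder. Its paragraph opens by saying that the assessments address conditions that often accompany aMCI. Section 2.0 names these as depression, anxiety, apathy and disturbed sleep, and Section 3.0 puts comorbid depression at 25-40%. On that reading the sentence simply keeps ordinary comorbidity in the trial. Section 5.0 is the formal list, with someone charged with enforcing it. Record review, the clinical evaluation required by inclusion criterion v and the TMS safety screen (repeated at Session 1) should catch most documented cases, although the documents do not show the items of that screen. Section 14.0 then allows removal before Session 3.

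Most of this stands. The intended rule is probably Section 5.0, and the affected group is small. What remains is that the sentence is worded as a general exclusion rule, the protocol states no order of precedence, and the Section 14.0 power is discretionary. If Section 5.0 governs, the Session 1 sentence is wrong as written.

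A reader might infer more than the documents support:

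- **That the protocol deliberately admits bipolar patients, or type II patients.** Section 10.0 never names the condition, and Section 15.0 is only silent on type II.
- **That staff are told such a participant is not a protocol violation.** Section 10.0 says nothing about violations, and a participant who meets criterion iv could still be discontinued on that ground.
- **That bipolar disorder is the only Section 5.0 condition missing from the Session 1 exception.** Criterion iii gives its severe mental illnesses as examples, so the list is open, and it also names developmental disorder.

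**Conclusion.** The inconsistency is real and should be corrected. For bipolar disorder first detected at Session 1, three sections give three scopes: any type excluded (Section 5.0 iv), not excluded on a literal reading (Section 10.0), and type I excluded (Section 15.0). The consequence of following the Session 1 sentence literally is a full course of 24 sessions in a participant with a listed contraindication.

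The size is limited. Only cases not already in the medical record are affected, a discretionary safeguard exists before treatment, and no endpoint, analysis or sample size changes. The conclusion rests on the literal wording of the Session 1 sentence and on the absence of a precedence rule. It assumes nothing about how common such cases are.

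**What to change.** Make two wording edits.

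1. **Section 10.0, Session 1.** Replace the sentence with a reference to the eligibility list, for example: *A neuropsychiatric condition found at Session 1 excludes the participant, before any rTMS, if it meets a Section 5.0 exclusion criterion; these include psychotic disorders, bipolar disorder of any type and substance use disorders. Other neuropsychiatric conditions do not exclude.* The cross-reference is better than adding bipolar disorder to the existing exception, because it also keeps the other Section 5.0 conditions aligned.
2. **Section 15.0.** Change bipolar type I to bipolar disorder.

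No new procedure is needed, since the M.I.N.I. and the mania scale are already given at Session 1. The downside is that a candidate will occasionally be lost after consent. Planned enrolment leaves a margin of 40 − 30 = 10 over the completer target. Such a case should be counted as a screen failure. If it stayed in a retention denominator of 40, each one would cost 1/40 = 2.5 percentage points against the target of more than 80%.
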